#### 7.1. Critical Baseline Assessments

Baseline assessments comprise clinical examination with detailed skin examination and standardised skin photos (face, trunk, limbs, scalp, nails, hand and feet). The dermatologic assessment will be reproduced at each biomarker sampling at week 2, 8, 10 and at disease progression. Efficacy assessments conducted at baseline are described in Section 7.3.2, tumour tissue and biomarker assessments are described in Section 7.2. Safety assessments conducted at baseline and during treatment are described in Section 7.4. Cardiovascular medical history/risk factors will be assessed at baseline.

#### 7.1.1. BRAF Mutation Determination

The conduct of the BRAF-mutation screening prior to the baseline assessments is the responsibility of the investigator and must be performed in a local laboratory. Testing for BRAF mutation for enrolment in the trial can occur any time prior to dosing.

## 7.1.2. Baseline Documentation of Target and Non-target Lesions

All baseline lesion assessments, including brain MRI/CT to rule out brain metastases, must be performed within 5 weeks prior to randomisation.

- Lymph nodes that have a short axis of < 10 mm are considered non-pathological and should not be recorded or followed.
- Pathological lymph nodes with a short axis of < 15 mm but ≥ 10 mm are considered non-measurable.
- Pathological lymph nodes with a short axis of ≥ 15 mm are considered measurable and can be selected as target lesions. Lymph nodes should not be selected as target lesions when other suitable target lesions are available.
- Measurable lesions up to a maximum of 2 lesions per organ and 5 lesions in total, representative of all involved organs, should be identified as target lesions, and recorded and measured at baseline. These lesions should be selected on the basis of their size (i.e., lesions with the longest diameter) and their suitability for accurate repeated measurements (i.e., either by imaging techniques or clinically).

**Note**: Cystic lesions thought to represent cystic metastases should not be selected as target lesions when other suitable target lesions are available.

**Note**: Measurable lesions that have been previously irradiated and have not been shown to be progressing following irradiation should not be considered as target lesions.

 Lytic bone lesions or mixed lytic-blastic lesions, with identifiable soft tissue components, that can be evaluated by CT or MRI can be considered measurable. Bone scans, fluorodeoxyglucose positron emission tomography (FDG-PET) scans or X-rays are not considered adequate imaging techniques to measure bone lesions. • All other lesions (or sites of disease) should be identified as non-target and should also be recorded at baseline. Non-target lesions will be grouped by organ. Measurements of these lesions are not required, but the presence or absence of each should be noted throughout follow-up.

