#### 4.1.2. Inclusion Criteria

Specific information regarding warnings, precautions, contraindications, adverse events, and other pertinent information on the GSK investigational products dabrafenib (GSK2118436) and trametinib (GSK1120212) that may impact patient eligibility is provided in the Investigator Brochures (IBs).

Deviations from inclusion criteria are not allowed because they can potentially jeopardize the scientific integrity of the study, regulatory acceptability or patient safety. Therefore, adherence to the criteria as specified in the protocol is essential.

Patients eligible for enrolment in the study must meet all of the following criteria:

- 1. Signed written informed consent;
- 2.  $\geq$ 18 years of age;
- 3. Histologically confirmed cutaneous melanoma that is either Stage IIIc (unresectable) or Stage IV (metastatic) (according to American Joint Committee on Cancer (AJCC) staging 7th edition).
- 4. BRAF V600E/K mutation-positive confirmed by a local laboratory.
- 5. Accessible melanoma tumours for biopsies (locally advanced primary melanoma or metastases)
- 6. Measurable disease according to Response Evaluation Criteria in Solid Tumours (RECIST 1.1) (Eisenhauer, 2009) on not biopsied lesions. Refer to Section 7.3.3.1 for the definition of a measureable lesion.
- 7. All prior anti-cancer treatment-related toxicities (except alopecia) must be ≤ Grade 1 according to the Common Terminology Criteria for Adverse Events version 4 (CTCAE version 4.0) at the time of randomisation.
- 8. Able to swallow and retain orally administered medication and does not have any clinically significant gastrointestinal abnormalities that may alter absorption such as malabsorption syndrome or major resection of the stomach or bowels.
- 9. Women of childbearing potential must have a negative serum pregnancy test within 14 days prior to randomisation and agree to use effective contraception, as defined in Section 7.4.3.1, throughout the treatment period, and for 4 months after the last dose of study treatment.

- 10. Eastern Cooperative Oncology Group (ECOG) Performance Status score of 0 or 1. Refer to Appendix 1 for details.
- 11. Adequate baseline organ function as defined in Table 2.

 Table 2
 Definitions for Adequate Baseline Organ Function

System	Laboratory Values
Hematologic	
ANC	$\geq 1.2 \times 10^9 / L$
Haemoglobin	≥ 9 g/dL
Platelet count	$\geq$ 75 x 10 $^{9}$ /L
PT/INR and PTT a	≤ 1.5 x ULN
Hepatic	
Albumin	≥ 2.5 g/dL

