- 5. Baseline MRI (preferred) or CT (only if MRI contraindicated or unavailable) of the brain must be performed on all patients to rule out current leptomeningeal metastases, brain metastases, or spinal cord compression secondary to metastasis. Post-baseline scans should be performed in all patients with documented metastases at baseline and as clinically indicated (e.g., symptoms suggestive of CNS progression) in all patients.
- 6. Lesion assessments must be done for chest, abdomen, pelvis, and any area of known disease. Lesion assessment by contrast CT (preferred) or MRI must be performed within 5 weeks prior to randomisation and at the times indicated until disease progression, death, or withdrawal of consent, whichever occurs first. (See Section 7.3.3 for instructions regarding chest X-Rays and CT assessment.) Target and non-target lesions must be identified at the time of screening and the same lesions must be re-assessed at each timepoint in a consistent manner according to RECIST, version 1.1. The same diagnostic method, including use of contrast when applicable, must be used throughout the study to evaluate each lesion. Lesion measurements will be taken using ruler or calipers. The Week 8 assessment for patients in arms A & B should be done before starting the combination treatment. If the last assessment was > 8 weeks prior to study withdrawal and disease progression had not been documented, a disease assessment should be obtained.

- 7. Randomisation will occur via RAMOS on Day 1.
- 8. Refer to Section 7.4.6 for details regarding vital sign measurements.
- 9. A complete physical examination will be performed at Screening and End-of-study; brief physical examinations will be performed at all other timepoints as indicated. In females, genitourinary exam should include a visual inspection of the cervix. If the patient has had a genitourinary and rectal exam within 6 months of screening the genitourinary and rectal exam do not need to be repeated. Refer to Section 7.4.7 for details.
- 10. An ophthalmic examination will be performed at Screening; additional ophthalmic examinations will be performed only as symptomatically warranted. Refer to Section 7.4.5 for details.

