#### 7.2. Biomarkers

Comparative examination of pre-dosing profiles of patients may uncover known or novel candidate biomarkers/profiles which could be used to predict response to study treatments or provide new insights into melanoma and medically related conditions. Comparative examination of post-dosing profiles in conjunction with pre-dosing profiles may yield known and novel candidate biomarkers/profiles and new insights which relate to the action of the study treatments and changes contributing to the development of resistance.

Novel candidate biomarkers and subsequently discovered biomarkers of the biological response associated with melanoma or medically related conditions and/or the action of the study treatments may be identified by application of DNA/gene, RNA and protein analysis of tumour tissue.

Unless stated otherwise, these investigations may be performed irrespective of whether a response to study treatment is observed.

Biopsies will be performed on cutaneous or sub-cutaneous lesions that are easily accessible and will NOT be performed on any deep lesions. If possible biopsies should be taken from the same lesion/location. Key biopsies are taken at randomisation, week 2, week 8, and week 10. Additional patients might be recruited to ensure a sufficient number of patients in each arm providing these three key biopsies.

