#### Measurable disease:

The presence of at least one measurable lesion. Palpable lesions that are not measurable by radiologic or photographic evaluations may not be used as the only measurable lesion.

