11.2.2.1. Change from baseline

Depending upon data availability, exploratory analyses may be performed to examine potential relationships between decrease from baseline H-score from tumor biopsies, and tumor response.

Tumor response will be quantified using change from baseline of tumor measurements (% change sum of lesion diameters [SLD]). Percent change from baseline for sum of lesion diameters is set to missing if any target lesions at baseline are missing or not measured at post baseline observation. Correlation between decrease in H-score and %SLD will be evaluated using Spearman's correlation coefficient. A scatter plot will be created for each treatment arm.

Summaries of the relationship between change in H-score and CR/PR/ Stable Disease (SD)/ Progressive Disease (PD) (without confirmation) will be assessed if data permit (i.e. if there are enough subjects with CR, PR etc.).

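### Target-lesion selection does not exclude biopsied lesions, so tissue removed by biopsy can be scored as tumour shrinkage

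*Protocol*

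**What the plan says.** **Entry.** Protocol Section 4.1.2, criterion 6, requires "Measurable disease according to Response Evaluation Criteria in Solid Tumours (RECIST 1.1) (Eisenhauer, 2009) on not biopsied lesions". Section 7.3.3.1 defines measurable disease as "The presence of at least one measurable lesion".

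**Target selection.** Section 7.1.2 takes measurable lesions "up to a maximum of 2 lesions per organ and 5 lesions in total, representative of all involved organs" and adds: "These lesions should be selected on the basis of their size (i.e., lesions with the longest diameter) and their suitability for accurate repeated measurements". It restricts the use of lymph nodes, cystic lesions and irradiated lesions. It does not mention biopsied lesions. Under Section 7.3.3.1, a skin lesion of at least 10 mm by caliper or photograph is measurable.

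**Biopsies.** Section 7.2 limits them to cutaneous or subcutaneous lesions that are easy to reach, and plans them at randomisation and Weeks 2, 8 and 10. It adds: "If possible biopsies should be taken from the same lesion/location". Footnote 22 of the Time and Events table (Table 19) leaves each biopsy to the investigator's judgement.

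**Timing.** Footnote 6 of Table 19 states: "Target and non-target lesions must be identified at the time of screening". SAP Section 9.2.7 takes the lesion baseline from screening and the tumour-biopsy baseline from Day 1.

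**Analysis.** SAP Section 13.2 counts confirmed and unconfirmed responses by investigator assessment. SAP Section 11.2.2.1 correlates the change in p-ERK H-score with percentage change in the sum of lesion diameters (%SLD). It sets %SLD to missing only when a target is missing or not measured.

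**The concern.** Criterion 6 shows that the sponsor meant response to be measurable away from the biopsy site. It is an entry condition, however. One non-biopsied measurable lesion satisfies it, even if a second lesion that is being biopsied is also a target. Section 7.1.2 is where the separation would have to be enforced, and it is silent there.

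The two groups of lesions overlap. A superficial nodule of 10 mm or more is an allowed biopsy site and a valid target, and the aim of covering all involved organs can bring it into the target set.

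If that happens, tissue removed after screening can be read as tumour shrinkage in ORR and the waterfall plots. The p-ERK correlation is the most exposed, because the lesion supplying the H-score would also be altering the clinical variable it is correlated with. That matters for a trial whose primary objective is to find biomarkers linked to response.

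**Working it through.** The plan states no figure on this point, so there is none to reproduce. The check is a reading of the timeline followed by RECIST arithmetic.

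**Sequence for a lesion that is both target and biopsy site**
1. Baseline diameter: screening, up to 5 weeks before randomisation.
2. Biopsies: Day 1 and Week 2.
3. First scheduled response assessment: Week 8, after at least two planned biopsies.
4. Biopsies: Weeks 8 and 10.
5. Next assessment: Week 16, after all four. The final analysis follows the last patient's Week 16 assessment (protocol Section 9.3.5).

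All removed tissue therefore falls after the RECIST baseline.

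**Inputs**
- PR threshold: a fall of at least 30% in the sum of diameters (protocol Section 7.3.4.1).
- Up to 5 targets (Section 7.1.2).
- 54 patients randomised 1:1:1, so 18 per arm (Section 4.1.1).
- Assumption: *k* targets of equal diameter, one of them biopsied.

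**No drug effect.** If the biopsied lesion loses a fraction *f* of its diameter, the sum falls by *f/k*. A PR needs *f* ≥ 0.30*k*.

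| Targets | Loss needed for PR | Maximum fall in sum |
|---|---|---|
| 2 | 60% | 50% |
| 3 | 90% | 33.3% |
| 4 | not possible | 25% |
| 5 | not possible | 20% |

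With a single target, 30% would be enough. That case does not arise if the non-biopsied lesion required by criterion 6 is itself a target.

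**Drug shrinkage *s* on every target.** The further fraction *g* of the biopsied lesion's remaining diameter needed for PR is *g* = *k*(0.30 − *s*)/(1 − *s*). For *s* = 0.20:
- *k* = 2: 2 × 0.10/0.80 = 25%
- *k* = 3: 3 × 0.10/0.80 = 37.5%

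**In millimetres.** The documents give no tissue loss. Assume 3 to 8 mm of diameter lost from one of *k* lesions of 15 mm each, so the fall is loss/(15*k*):
- *k* = 2: 3/30 = 10% to 8/30 = 26.7%
- *k* = 5: 3/75 = 4% to 8/75 = 10.7%

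None of these reaches 30% alone. Each could carry a patient over the threshold when added to real shrinkage.

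**Effect on ORR.** One patient is 1/18 = 5.6 points. For example, 9/18 = 50.0% (Clopper-Pearson 95% CI 26.0 to 74.0) becomes 10/18 = 55.6% (30.8 to 78.5).

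**The case against.** The strongest reply is that the documents already point the right way. Criterion 6 allows no deviation, and a nodule due for serial biopsy is arguably a poor fit with the requirement for accurate repeated measurement. That is a reasonable reading, but so is the opposite one, since a photographed skin nodule is easy to remeasure. Sites may therefore differ.

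Other rules might catch the problem. The notes to protocol Section 7.3.4.1 make response not evaluable (unless PD is shown) when not all baseline targets are assessed. SAP Section 11.2.2.1 sets %SLD to missing in that case. SAP Section 9.2.5 can count cancer-related surgery as new anti-cancer therapy. None of these names biopsy. A partly sampled lesion is still measured, and one judged to have disappeared is recorded as 0 mm. Scans are not centrally reviewed.

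A reader might infer that biopsy tissue will be scored as response. For example, losing a 20 mm nodule from a 60 mm sum gives (60 − 20)/60 = 66.7% of baseline, a fall of 33% and so a PR. The documents do not support that as the expected course. They give no biopsy type or size, ask that the impact on patients be kept small, allow ultrasound-led biopsy, and leave each biopsy to judgement. A lesion removed early could not supply the later samples, so whole-lesion loss fits poorly with four serial samples.

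It also stands that the affected outputs are descriptive secondary or exploratory ones, and that all arms share the same biopsy schedule.

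**Conclusion.** The gap is real and the bias is conditional. It needs a site to choose the biopsied lesion as a target, and sampling to shorten its measured diameter. The documents permit the first and give no information on the second.

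Under equal-sized targets, biopsy alone produces a PR only with large losses (60% or 90%), and only with two or three targets. Combined with a 20% drug effect and two targets, a 25% further loss is enough. Each misclassified patient costs 5.6 points of ORR in an arm. How many patients would be affected cannot be estimated from the documents.

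A reader might also infer that PFS and DoR are lengthened. That does not follow. A smaller sum lowers the nadir and could bring progression forward, scarring or inflammation could mimic growth, and the net direction is unclear.

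This should be corrected because the remedy is cheap and the p-ERK correlation is directly exposed. It does not show that the planned results would be wrong.

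**What to change.** 1. **Protocol 7.1.2.** Add: *A lesion that has been biopsied, or is planned for biopsy, must not be selected as a target lesion; record it as non-target.* Because targets are fixed at screening, the intended biopsy lesion has to be named then too.
2. **eCRF.** Record which lesion was biopsied at each time point.
3. **SAP 11.2.2 and 13.2.** For patients already enrolled with a biopsied target, recompute the sum of diameters and the response with that lesion left out at baseline and all later visits. Report ORR, the waterfall plots and the p-ERK correlation both ways.

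The cost is one protocol sentence, one eCRF field and one extra derivation. Some patients will have fewer target lesions, so their sums will be less precise. No patient loses eligibility, because criterion 6 already requires measurable disease on a non-biopsied lesion. The sample size does not change.

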#### 7.2. Biomarkers

Comparative examination of pre-dosing profiles of patients may uncover known or novel candidate biomarkers/profiles which could be used to predict response to study treatments or provide new insights into melanoma and medically related conditions. Comparative examination of post-dosing profiles in conjunction with pre-dosing profiles may yield known and novel candidate biomarkers/profiles and new insights which relate to the action of the study treatments and changes contributing to the development of resistance.

Novel candidate biomarkers and subsequently discovered biomarkers of the biological response associated with melanoma or medically related conditions and/or the action of the study treatments may be identified by application of DNA/gene, RNA and protein analysis of tumour tissue.

Unless stated otherwise, these investigations may be performed irrespective of whether a response to study treatment is observed.

Biopsies will be performed on cutaneous or sub-cutaneous lesions that are easily accessible and will NOT be performed on any deep lesions. If possible biopsies should be taken from the same lesion/location. Key biopsies are taken at randomisation, week 2, week 8, and week 10. Additional patients might be recruited to ensure a sufficient number of patients in each arm providing these three key biopsies.

### 7.2.1. Biomarkers on blood sample

Biomarkers include, but are not limited to:

- LDH
- CRP
- Osteopontin
- Circulating cell-free DNA (cfDNA)
- Protein S 100
- Lymphocyte subpopulations
- Inflammatory cytokines (e.g. TNF-α, IL-1)

## 7.2.2. Biomarkers on tumour sample

The exploratory research objectives of this study include further characterisation of the patient population through analysis of tumour DNA, RNA and protein, or other aberrations from tumour tissue and to determine whether these are associated with clinical outcome in response to therapy and/or to toxicity.

## Biomarkers in the melanoma tumour samples:

Biomarkers include, but are not limited to:

Immunohistochemistry (IHC) on fixed tumour samples:

- P-ERK
- P-MEK
- Ki-67
- P-AKT
- P-S6
- PTEN
- eIF4E and P-eIF4E
- eIF4G
- CDK4
- c-Met
- EGFR
- P-EGFR

## Mutations screening:

A panel of genes relevant in melanoma biology (up to 400 genes potentially involved ontogeny or resistance) such as *BRAF*, *MEK1* and 2, *HRAS*, *NRAS*, *KRAS*, *PTEN*, *KIT*, *NRAS*, *STK11*, *TP53*, *MNK1 CDK4*, *CDKN2ATGFBR1*, *EGF* will be assessed on limited quantity of DNA using IonTorrent technology. This analysis should allow a sensitivity of mutation detection up to 10% of mutated DNA extracted from FFPE or frozen samples collected at base line or after (e.g. at recurrence).

For samples with sufficient amount of DNA, according to method available (currently  $3\mu g$ ) the whole exome analysis will be performed.

Additional analysis of chromosomal abnormalities by CGH array and transcriptome analysis with Gen Expression microarray will be performed on frozen samples

# Biomarkers in skin tumours induced by kinase inhibitors (papillomas, KA and SCC):

Biomarkers include, but are not limited to:

- Fixed samples: P-ERK and P-MEK
- Mutations screening: mutational hotspot for the three *RAS* genes, *TGFBR1*, *TP53*, *BRAF*
- HPV DNA and RNA

## 7.2.3. Biomarkers on skin sample

Biomarkers include, but are not limited to:

- Fixes samples: P-ERK, P-MEK, P-AKT, eiF4E and P-eiF4E, P-S6, HPV DNA, Ki-67
- Frozen samples: kinome analysis

# 7.3. Efficacy

# 7.3.1. Efficacy Endpoints

The efficacy endpoints of this study are:

- Overall response rate (ORR), defined as the percentage of patients with a confirmed or unconfirmed CR or PR at any time per RECIST, version 1.1 (Eisenhauer, 2009).
- Progression-free survival (PFS), defined as the time from randomisation until the earliest date of disease progression or death due to any cause.
- Duration of response, defined as the time from first documented evidence of CR or PR until disease progression or death due to any cause among patients who achieve an overall response (i.e., unconfirmed or confirmed CR or PR)

# 7.3.2. Efficacy Assessment

Disease progression and response evaluations will be determined according to the definitions established in RECIST version 1.1 (Eisenhauer, 2009).

Refer to the Time and Events table (Table 19) for the schedule of efficacy assessments. Assessments must be performed on a calendar schedule and should not be affected by dose interruptions/delays.

The following scans/assessments are required at baseline: contrast CT (preferred method) of chest/abdomen/pelvis or MRI of abdomen/pelvis and any area of known disease, skin lesion photography, and clinical disease assessment for palpable lesions. Exception: If a chest CT cannot be performed, chest X-ray can be used only to document **the absence of disease** (no tumour lesions) or the **presence of new lesions**. If lesions are detected at baseline by chest X-ray, chest CT must be done to properly document these lesions at baseline and in follow-up tumour assessments. At each post-baseline assessment, evaluations of the sites of disease identified by these scans are required.

A brain MRI (preferred) or CT scan is required for all patients at baseline to rule out brain metastases. If clinically indicated, a CT or MRI scan of affected bone areas will be required at baseline. Bone lesions, if present, will continue to be followed consistently throughout the study until disease progression, death, or withdrawal of consent.

Confirmation of response (i.e., CR and PR) is not necessary per RECIST, version 1.1, as the primary endpoint of the study is not overall best response.

Scans will be assessed by investigators and will not be collected for central review.

